Cover Page:

Title: Evaluation of AI-based Risk Assessment Model in Plastic Surgery

NCT Number: [NCT ID not yet assigned]

Document Date: July 11, 2024

Document Review Statement:

This document was most recently updated and reviewed by the sole researcher, [name], EMBA, on July 11, 2024. As there is no human subjects protection review board required for this study, this date reflects the most recent review and update by the principal investigator.

Study Protocol

Introduction

This study protocol outlines the procedures, objectives, and methodologies for the observational study titled "Evaluation of AI-based Risk Assessment Model in Plastic Surgery." The primary aim is to evaluate the clinical utility of an AI-based risk assessment model in predicting and mitigating complications in patients undergoing elective plastic surgery.

Study Objectives

- To evaluate the effectiveness of the AI-based risk assessment model in predicting surgical complications.
- To determine the correlation between various clinical factors (such as BMI, age, and smoking habits) and the AI-generated risk scores.
- To assess the impact of AI-generated recommendations on surgical outcomes and complication rates.

Study Design

This is an observational study with a prospective time perspective. The study involves the collection of clinical data from patients undergoing elective plastic surgery. The AI model analyzes this data to provide personalized risk scores and recommendations.

Participant Eligibility

Inclusion Criteria:

- Individuals aged 18 and older.
- Scheduled to undergo elective plastic surgery.
- Agreement to follow preoperative and postoperative recommendations provided by [name], according to the AI-based risk assessment model.

Exclusion Criteria:

- Individuals below 18 years of age.
- Patients with a history of severe allergic reactions to anesthesia.
- Those unable to provide informed consent.

Study Population Description

Participants are individuals undergoing elective plastic surgery. They will complete an online form collecting data on various clinical factors, such as age, height, weight, smoking habits, and comorbidities. The system calculates the risk score, body mass index (BMI), and Caprini score.

Data Collection

The following data will be collected from each participant:

- Age
- Height and weight (to calculate BMI)
- Smoking habits
- Comorbidities
- Caprini score (calculated by the system)

- Risk group classification (High, Moderate, Low)
- Complications (Hematoma, Seroma, Infection, Dehiscence, Necrosis, DVT/PE, ASIA Syndrome)

Study Procedures

Participants will undergo a risk assessment using the AI model, which evaluates multiple risk factors based on their clinical data and patient history. The model will then generate personalized recommendations, which include:

- Weight management guidance for patients with a BMI greater than 25.1.
- Smoking cessation advice for patients who smoke.
- Blood pressure control recommendations for hypertensive patients.
- Doppler ultrasound screening for deep vein thrombosis (DVT) and varices.
- Nutritional consultations for patients with a BMI of 25.1 or lower.
- Specialist referrals based on comorbidities and psychiatric consultations for Body Dysmorphic Disorder (BDD) screening.

Follow-Up

The follow-up period for this study ranges from 2 to 41 months, with a mean follow-up of 15 months. During this time, data on patient outcomes, including complication rates and patient satisfaction, will be collected and analyzed.

Outcome Measures

Primary Outcome Measure

Title: Incidence of complications within 45 days post-surgery

Description: The primary outcome measure is the incidence of complications (such as hematoma, seroma, infection, etc.) occurring within 45 days after elective plastic surgery. Complications are identified and recorded based on clinical follow-up visits and patient reports.

Conclusion

This study protocol provides a comprehensive overview of the study design, objectives, data collection methods, and statistical analysis plan for the observational study "Evaluation of AI-based Risk Assessment Model in Plastic Surgery." The integration of AI-generated recommendations is expected to enhance preoperative planning and postoperative care, ultimately improving patient safety and satisfaction.

Statistical Analysis Plan (SAP)

Introduction

This Statistical Analysis Plan (SAP) outlines the statistical methods and analyses to be performed for the study titled "Evaluation of AI-based Risk Assessment Model in Plastic Surgery." The primary aim of the study is to assess the clinical utility of an AI-based risk assessment model in identifying and mitigating risk factors associated with complications in patients undergoing elective plastic surgery.

Study Objectives

- To evaluate the effectiveness of the AI-based risk assessment model in predicting surgical complications.
- To determine the correlation between various clinical factors (such as BMI, age, and smoking habits) and the AI-generated risk scores.
- To assess the impact of AI-generated recommendations on surgical outcomes and complication rates.

Study Design

This is an observational study with a prospective time perspective. The study involves the collection of clinical data from patients undergoing elective plastic surgery. The AI model analyzes this data to provide personalized risk scores and recommendations.

Data Collection

The following data will be collected from each participant:

- Age
- Height and weight (to calculate BMI)
- Smoking habits
- Comorbidities
- Caprini score (calculated by the system)
- Risk group classification (High, Moderate, Low)
- Complications (Hematoma, Seroma, Infection, Dehiscence, Necrosis, DVT/PE, ASIA Syndrome)

Primary Outcome Measure

Title: Incidence of complications within 45 days post-surgery

Description: The primary outcome measure is the incidence of complications (such as hematoma, seroma, infection, etc.) occurring within 45 days after elective plastic surgery. Complications are identified and recorded based on clinical follow-up visits and patient reports.

Statistical Methods

The following statistical methods and formulas will be used for data analysis:

Descriptive Statistics:

- Frequency and percentage of patients in each risk group (High, Moderate, Low)
- Incidence of complications in each risk group

- Relative risk and odds ratio for complications in each risk group

Pearson Correlation:

- Correlation between risk factors (Age, BMI, Smoking habits, etc.) and AI-generated risk scores

python

Copiar código

```
stats.pearsonr(corr4['Risk factor'], corr4['BMI'])

stats.pearsonr(corr4['Risk factor'], corr4['Caprini score'])

stats.pearsonr(corr4['Risk factor'], corr4['Age'])

stats.pearsonr(corr4['Risk factor'], corr4['Smoking habit'])

stats.pearsonr(corr4['Risk factor'], corr4['Male'])

stats.pearsonr(corr4['Risk factor'], corr4['Female'])

stats.pearsonr(corr4['Risk factor'], corr4['High blood pressure'])
```

Outcome Analysis:

- Count and percentage of complications in each risk group
- Calculation of relative risk and odds ratio

python

Copiar código

Relative Risk = (Incidence in high-risk group) / (Incidence in low-risk group)

Odds Ratio = (Odds of complications in high-risk group) / (Odds of complications in low-risk group)

Data Analysis

Data analysis will be performed using Python, and the complete notebook with the analysis code and results is available at the following link: [Colab Notebook](#).

Access Instructions

To request permission to access the individual participant data (IPD) and supporting information, please email [contact]. Detailed instructions for requesting access can be found at [IPD Sharing Instructions](#).

Conclusion

This SAP provides a detailed plan for the statistical analysis of the study "Evaluation of AI-based Risk Assessment Model in Plastic Surgery." The analysis aims to provide insights into the effectiveness of the AI model in predicting and mitigating surgical complications, ultimately improving patient outcomes and safety.

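### The plan sets an objective on the impact of the AI recommendations, but names no comparator or reference rate and specifies no analysis that could show impact

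*Combined protocol and SAP*

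**What the plan says.** Study Objectives, in both the protocol and the SAP, include "To assess the impact of AI-generated recommendations on surgical outcomes and complication rates". The protocol's Introduction gives the primary aim as evaluating the model's clinical utility "in predicting and mitigating complications in patients undergoing elective plastic surgery". The SAP's Conclusion again pairs prediction with mitigation and looks ahead to better outcomes and safety.

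On exposure, an inclusion criterion under Participant Eligibility begins "Agreement to follow preoperative and postoperative recommendations provided by" and ties those recommendations to the AI model. The Data Collection lists in both parts cover baseline factors, Caprini score, risk group and complications. They have no entry for recommendations issued or followed.

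On analysis, the SAP's Statistical Methods list the frequency of each risk group, "Incidence of complications in each risk group", "Relative risk and odds ratio for complications in each risk group", formulas that set the high-risk group against the low-risk group, and Pearson correlations of the risk score with baseline factors. The SAP's Data Analysis section points to an external notebook of code and results, which is not among the documents.

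**The concern.** Impact and mitigation are statements about effect. They need some account of what the complication rate would have been without the recommendations: a concurrent group, a historical or external series, or at least a justified reference rate. The plan names none of these. Because agreement to follow the advice is a condition of entry, the cohort has no planned unexposed group, and because issue and uptake are not recorded, an internal comparison by uptake has no listed variable either.

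At stake is what the study may conclude. If the plan is followed exactly, the analyst ends with complication rates by risk stratum. A low rate could then be read as evidence that the tool prevents complications, and nothing in the plan rules that reading out. The 45-day incidence and every listed analysis can still be carried out; what fails is the step from those results to impact.

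**Working it through.** The documents state no complication rate, sample size, effect size or margin, so there is no planned figure to reproduce. The check has two parts.

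**1. Does any listed analysis contrast the recommendations?**

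| Analysis in the SAP text | What it compares | Bears on impact? |
|---|---|---|
| Risk-group frequencies | Nothing; describes the cohort | No |
| Complication counts, percentages and incidence by risk group | The model's own strata | No |
| Relative risk (RR) and odds ratio (OR) | High-risk against low-risk stratum | No; informs prediction |
| Pearson correlations | Risk score against baseline factors | No; uses neither complications nor recommendations |

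**2. Could the planned results carry the effect anyway?** All rates below are assumed. They show that the effect is not identifiable; they do not estimate a bias.

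Let m be the risk with recommendations divided by the risk without, first taken as equal in both groups.

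*Backward: observed incidence fixed at 10% (high) and 5% (low).* RR = 0.10/0.05 = 2.0. OR = (0.10/0.90)/(0.05/0.95) = 2.11. Risk without recommendations = observed/m.

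| m | Risk without, high/low | Change due to recommendations, high/low (percentage points) |
|---|---|---|
| 0.5 | 20% / 10% | -10 / -5 (benefit) |
| 1 | 10% / 5% | 0 / 0 (no effect) |
| 2 | 5% / 2.5% | +5 / +2.5 (harm) |

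The same data fit all three rows.

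*Forward: risk without recommendations fixed at 10% and 5%.*

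| m | Observed, high/low | RR | OR |
|---|---|---|---|
| 0.5 | 5% / 2.5% | 2.0 | (0.05/0.95)/(0.025/0.975) = 2.05 |
| 1 | 10% / 5% | 2.0 | 2.11 |
| 2 | 20% / 10% | 2.0 | (0.20/0.80)/(0.10/0.90) = 2.25 |

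With equal m the RR is (m·pH)/(m·pL) = pH/pL, where pH and pL are the high- and low-risk rates without recommendations; m cancels. The incidences move, and the OR moves a little, but neither can be interpreted without the unexposed rates.

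*Unequal effects.* From 10%/5%, halving only the high-risk rate gives 5%/5% and RR = 1.0, so the RR does move. It still cannot be read as impact. An observed RR of 2.0 arises from halving the high-risk rate alone (20% to 10%, against 5%), from no effect (10% against 5%), and from 20% relative harm in both groups (10%/5% to 12%/6%).

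**The case against.** The strongest reply is that this is an observational study whose primary outcome is an incidence, that RR and OR already sit under descriptive statistics, and that no success criterion or test of benefit is stated. All of that is true, and a purely descriptive cohort would need no comparator. But the plan also sets an impact objective and puts mitigation in its primary aim, and describing the cohort does not answer either.

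A second reply is that the high- against low-risk contrast is itself the comparison. It is not one on recommendations: patients in both strata enter on the same agreement to follow them, so the contrast speaks to stratification.

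A third is that the notebook may contain the missing comparison. That stands as a limit. A reader might infer that no comparator exists; the documents show only that none is named.

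A reader might also infer that every participant was managed under the recommendations, since "Weight management guidance for patients with a BMI greater than 25.1" and "Nutritional consultations for patients with a BMI of 25.1 or lower" together span every BMI. The documents require agreement only and list no record of receipt or adherence, so this is not established, and the point does not need it.

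Finally, it is fair to say that an unchanged RR is a special case. Several recommendations are tied to particular risk factors, so unequal effects are plausible. The working shows that they do not rescue the inference.

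**Conclusion.** The concern holds for the SAP text. One of three objectives, and the mitigation half of the primary aim, cannot be answered with the data and analyses specified, because no contrast on recommendations and no reference rate is named. This should be corrected, since following the plan exactly cannot support the conclusion it aims at. No numerical bias can be attached: the rates used are assumed, and they show only that one set of results is compatible with benefit, no effect and harm. That conclusion does not depend on the effect being proportionally equal across risk groups.

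Two stronger readings are not supported. One is that the study as a whole fails; the 45-day incidence and the risk-group association remain estimable. The other is that the objective was written with outcomes in hand. The protocol's Follow-Up section reads like a summary of follow-up already completed ("The follow-up period for this study ranges from 2 to 41 months, with a mean follow-up of 15 months") and the SAP mentions existing results, but neither establishes when outcomes were examined relative to the objectives. It is a reason to ask, not a finding.

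**What to change.** Make the change by a dated, reasoned amendment.

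1. If the notebook or another source already holds a comparator or reference rate, name it in the SAP and specify the contrast with confounder adjustment, labelled non-randomised. Otherwise, record that the impact objective is not answerable with the specified data and analyses. State whether outcome data had been examined by then.
2. In the second case, replace the objective in both the protocol and the SAP with wording such as: *To describe how often complications occur in the 45 days after surgery, and how risk group is associated with them, in patients who agreed to follow the AI-generated recommendations.* State that other surgical outcomes, including the patient satisfaction mentioned under Follow-Up, are descriptive only, so that they are not dropped without comment.
3. Alongside this, remove the reference to mitigating from the aim in the protocol's Introduction and from the SAP's Conclusion, and remove the closing clause there about improved outcomes and safety. Limit the aim in the SAP's Introduction to identifying risk factors, since no repeat risk-factor measurement is listed.
4. Add to the SAP: *Risk-group incidences, RR and OR will not be used as evidence that the recommendations change complication rates.*

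The descriptive route costs wording changes in five places (two objectives, two aims, one conclusion), a few added sentences and no new data. Its price is a narrower claim, with one of three objectives openly recorded as not answered. Keeping an impact objective is not a cheap change, because the documents name no source for a comparator.

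### Does the promise to analyse patient satisfaction, with no outcome definition or method behind it, call for a change to the plan?

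*Combined protocol and SAP*

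**What the plan says.** The Follow-Up section of the protocol states: "The follow-up period for this study ranges from 2 to 41 months, with a mean follow-up of 15 months". It continues: "During this time, data on patient outcomes, including complication rates and patient satisfaction, will be collected and analyzed". The protocol's Conclusion returns to the subject once, expecting the AI recommendations to help care, "ultimately improving patient safety and satisfaction". These are the only two mentions of satisfaction in the document, and neither is in the SAP.

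The Data Collection sections of the protocol and the SAP open with the same line, "The following data will be collected from each participant", and give the same seven items. The only outcome among them is complications. Both parts define one outcome measure, "Incidence of complications within 45 days post-surgery", and no secondary outcome.

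The SAP's Statistical Methods section begins "The following statistical methods and formulas will be used for data analysis". It then gives risk-group frequencies, complication counts and incidence by risk group, relative risk and odds ratio (high against low), and Pearson correlations of the risk score with patient factors. The SAP's Conclusion says: "This SAP provides a detailed plan for the statistical analysis of the study".

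**The concern.** The Follow-Up sentence commits the study to both collecting and analysing satisfaction, while the SAP presents itself as the detailed plan and has no place for it. An analyst who followed the SAP to the letter would leave undone an analysis that the protocol announces. The instrument, the time point and the summary measure are all open.

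The usual stake with an undefined outcome is selective reporting. The mean follow-up of 15 months reads like an observed value, and the SAP's Data Analysis section says that "the complete notebook with the analysis code and results is available at the following link". If results were already known, a satisfaction result could be added or left out with nothing to check it against. The documents do not show that this happened.

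There is a second, smaller worry. The SAP's incidence, relative risk and odds ratio lines carry no time window of their own, while Follow-Up speaks of complication rates over a period of up to 41 months. If late events entered a simple relative risk, patients would have very unequal time at risk, and the SAP has no person-time or time-to-event method to allow for that.

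**Working it through.** The documents give no sample size, event count or design figure on this point, so there is nothing to reproduce. The check is mostly a comparison of sections.

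**1. Is satisfaction covered anywhere else?**

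| Place | Content | Satisfaction |
|---|---|---|
| Objectives (protocol and SAP) | prediction of complications; correlates of the score; effect of recommendations on outcomes and complication rates | not named |
| Primary aim (both introductions) | clinical utility for complications | not named |
| Data lists (both) | seven items each | absent |
| Outcome measures | one, complications to day 45 | absent |
| SAP methods | frequencies, incidence, relative risk, odds ratio, correlations | absent |

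The inconsistency is real. The data lists alone do not prove that satisfaction goes unrecorded: sex appears in the SAP's correlation code but in neither list, so the lists are not complete. What is certain is that no outcome definition and no method are given.

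**2. Does the gap reach any planned result?** The inputs to the relative risk and the odds ratio are the numbers of patients with and without complications in the high-risk and low-risk groups. The inputs to the correlations are the risk score and the patient factors. Satisfaction is an input to none of them, so its effect on each is zero.

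**3. Would a definition add a conclusion?** The Conclusion's expectation is that the recommendations improve satisfaction. Testing that needs patients without the recommendations, or some other reference. The inclusion criteria require every participant to agree to follow them, and no other group is described. A satisfaction summary by risk group would compare patients at different baseline risk, all of whom agreed to follow the recommendations. It would not address the expectation.

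**4. Which window applies to the complication analyses?** In the SAP, the 45-day outcome is the only one defined, and it comes immediately before Statistical Methods. Reading the complication lines as 45-day measures needs no extra assumption about the sponsor's intent.

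**5. Does the stated follow-up cover that window?** Take 30.4375 days per month and assume that follow-up is counted from surgery:

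- Shortest follow-up: 2 × 30.4375 = 60.9 days
- Margin beyond day 45: 60.9 − 45 = 15.9 days

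On that assumption everyone passes day 45, and unequal follow-up (41 / 2 = 20.5-fold from longest to shortest) does not disturb a 45-day proportion. The Follow-Up section does not state the starting point. If time were counted from the preoperative assessment, the margin would shrink by the wait for surgery, and coverage of day 45 could not be confirmed from the range alone. That question is separate from satisfaction.

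**The case for a change.** The best case for a change is that the sentence promises analysis as well as collection, and that two parts of one document should agree. The linked notebook cannot supply the missing plan: it is not among the documents, and it is said to contain results. The repair is also cheap: delete two phrases, or add a definition and one descriptive line. All of this is true as a description of the text.

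It could be added that the third objective speaks of surgical outcomes in general, which might be stretched to include satisfaction. But that objective specifies only complication rates, and the outcome section gives it only complications to work with.

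The step from inconsistency to required change does not stand. Deleting the phrases alters no analysis. Defining the outcome yields a descriptive summary that cannot test the hoped-for benefit. The selective-reporting argument rests on an inference from the mean follow-up and on a notebook whose content cannot be seen here. Even if a satisfaction figure did appear, its absence from the SAP already tells a reader that it was not a planned analysis.

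On later complications, the missing window in the SAP's lines is a fair remark about drafting. It would matter only if someone set aside the sole defined outcome in favour of the Follow-Up sentence.

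**Conclusion.** The observation is correct, but it does not call for a change. The protocol mentions an analysis of satisfaction that the SAP does not contain. This is a small completeness gap in a matter outside the stated objectives and primary aim. Its effect on the 45-day incidence, the relative risk, the odds ratio and the correlations is zero, because satisfaction is an input to none of them. Supplying a definition would bring no gain in what the study can conclude, since no group without the recommendations is described.

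Analysts can fill the gap sensibly: follow the SAP for the planned results, and label any satisfaction summary descriptive and exploratory. The complication lines are read as referring to the 45-day outcome, and whether later events are also described or compared is for the sponsor to decide.

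The conclusion on satisfaction rests on the written documents alone and needs no assumption about follow-up time. Only the side remark that all patients pass day 45 assumes that follow-up is counted from surgery.

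### The impact of the AI recommendations is an objective, but uptake is not specified as data, no analysis uses the recommendations and there is no comparator, so the objective can only be met descriptively

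*Combined protocol and SAP*

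**What the plan says.** The Study Objectives of both the protocol and the SAP include "To assess the impact of AI-generated recommendations on surgical outcomes and complication rates". The SAP Conclusion says the analysis will give insight into how well the model predicts and mitigates surgical complications.

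The protocol's Study Procedures describe the intervention: "The model will then generate personalized recommendations, which include" six kinds of item. Some carry explicit triggers, for example "Weight management guidance for patients with a BMI greater than 25.1" and "Smoking cessation advice for patients who smoke". Under Inclusion Criteria, entry requires "Agreement to follow preoperative and postoperative recommendations".

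The Data Collection sections of both documents open with "The following data will be collected from each participant" and give the same seven items: age, height and weight, smoking, comorbidities, Caprini score, risk group and complications. The protocol's Follow-Up section adds that "data on patient outcomes, including complication rates and patient satisfaction, will be collected and analyzed".

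The SAP's Statistical Methods consist of frequencies and complication incidence by risk group, seven Pearson correlations with the risk score, and a relative risk and odds ratio for the high- against the low-risk group.

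**The concern.** An objective about the impact of advice needs three things: a record of who was advised what, some knowledge of whether it was acted on, and a contrast that isolates the advice. The plan specifies part of the first, none of the second and none of the third.

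If the plan is followed as written, the study will report complication rates in patients who all agreed to take the advice. The SAP Conclusion then invites the reader to see those rates as evidence of mitigation. A low rate could reflect useful advice, a low-risk population or both. A high rate could reflect ineffective advice, advice not followed, or high underlying risk. The planned output could not tell these apart.

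**Working it through.** No figure in the plan bears on this point. The documents give no sample size, event rate, uptake or effect size, so the check consists of setting the sections side by side.

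**1. Data items.** Seven items appear on each list. Items recording that a recommendation was carried out: 0 of 7. Items recording that one was issued: 0 of 7. The Follow-Up section adds outcomes and satisfaction, not uptake.

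**2. What can be derived.** The six items in Study Procedures compare with the variables named in the plan as follows.

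| Recommendation | Trigger given | Issue derivable? | Completion specified? |
|---|---|---|---|
| Weight guidance | BMI above 25.1 | Yes, from height and weight | No |
| Nutritional consultation | BMI 25.1 or lower | Yes, from height and weight | No |
| Smoking cessation | Smoker | Yes, from smoking habits | No |
| Blood pressure control | Hypertensive | Yes; the SAP code has a high blood pressure column | No |
| Doppler screening | None written | Read literally, everyone | No |
| Specialist or psychiatric referral | Comorbidities, no exact rule | Not exactly | No |

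Issue can be derived from a stated trigger for four of six, is arguably universal for a fifth, and cannot be rebuilt exactly for the sixth. Completion is specified for none. For the four rule-based items, issue is fully determined by the trigger: under the rule, no patient above the BMI cut-off goes without weight guidance. An effect of that advice therefore cannot be separated from the effect of BMI.

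**3. Analyses.** The seven correlations pair the risk score with BMI, Caprini score, age, smoking, male, female and high blood pressure. The remaining analyses are counts, percentages, relative risk and odds ratio by risk group. Number using recommendations as a variable: 0.

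**4. What the one outcome contrast can show.** Let r_H and r_L be the complication risks without advice in the high- and low-risk groups, and let the advice multiply them by m_H and m_L. The planned ratio estimates

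RR = (r_H × m_H) / (r_L × m_L).

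If the advice works equally in both groups (m_H = m_L = m), m cancels and RR = r_H / r_L, whatever m is. If it works unequally, only the product is seen. The odds ratio does not cancel exactly, but it compares the same two groups, both of them advised. Incidence within one group estimates r × m, and without a comparator r is unknown. The contrast therefore describes how well the score separates patients, not what the advice does.

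**5. What uptake would add.** This illustration uses assumed values, none from the documents. Suppose advice has no effect in those who ignore it and baseline risk is the same in followers and non-followers. Then cohort-level reduction = uptake × effect in followers. With a 50% effect in followers:

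- 20% uptake: 0.2 × 0.5 = 0.10
- 80% uptake: 0.8 × 0.5 = 0.40

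A 20% reduction fits both 0.4 × 0.5 = 0.20 and 0.8 × 0.25 = 0.20. Uptake would help interpret a reduction, but this single-cohort plan cannot estimate the reduction in the first place.

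**The case against.** A reader might infer something stronger: that the intervention is not measured at all, and that missing adherence data are why nothing can be attributed to the advice. The documents do not support that, for four reasons.

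- **Issue is largely recoverable.** Four of the six recommendation types follow from stated triggers on variables the plan names, and the recommendations are themselves output of the model.
- **Not listed is not the same as not collected.** The lists are visibly incomplete. Sex and the risk score enter the SAP code and satisfaction appears under Follow-Up, yet none of these is on either list. The analysis notebook is linked but is not part of the documents. The safe statement is that uptake is not specified. Those other unlisted variables are at least named somewhere, whereas completion of advice is named nowhere.
- **Adherence is not a precondition for an effect estimate.** With a suitable comparator, the effect of being managed under the model's advice could be estimated as a policy effect without adherence data, because eligibility places every participant in the exposed group. The missing comparator is the main barrier. Uptake helps explain such an effect.
- **No text equates agreement with completion.** The inclusion criterion records an intention, and nothing in the SAP says it stands for delivery.

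Two practical objections also stand. Comparing patients who completed the advice with those who did not is open to adherer bias, so it cannot carry the objective. Follow-Up is also stated as a range of 2 to 41 months with a mean of 15, and the SAP says results are already in the notebook, which suggests that much of the data exists. If that range counts from surgery, even the shortest follow-up of about 60 days exceeds the 45-day outcome window. For those patients completion could be collected only after the outcome was known.

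None of this rescues the objective as worded. It still has no analysis, no comparator and no specified measure of uptake.

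**Conclusion.** The concern holds in this form: the plan sets the impact of the recommendations as an objective and promises insight into mitigation, but it specifies no data on whether advice was carried out, no analysis in which recommendations are a variable, and no comparator. Uptake cannot be described, and the planned results cannot show that the advice reduced complications.

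The reach is one objective of three, plus the mitigation half of the SAP Conclusion. The primary outcome, 45-day incidence, and its breakdown by risk group can still be estimated. No numerical bias can be given because the documents state no event rate or uptake.

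The conclusion assumes that the written plan is complete on uptake and comparators. If the linked notebook or the system already holds completion data, uptake could be described, but the absence of a comparator would still rule out a claim of effect. The plan should be changed on this point, though the comparator problem comes first.

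**What to change.** 1. Export the issued recommendations from the system for every participant and add them to both data lists. This also settles the referrals that cannot be rebuilt from the listed variables.
2. For patients not yet operated on or still in follow-up, add a completion field (yes, partly, no) for each recommendation type, covering both preoperative and postoperative advice. Record it before the complication outcome is known where possible, and flag entries made afterwards.
3. In the SAP, report issue and completion rates overall and by risk group, with the number missing.
4. Restate the third objective in both documents as a description of outcomes in patients managed under the recommendations, with no claim of effect. Reword the mitigation statement in the SAP Conclusion to match, and align the similar aim statements in the two Introductions.
5. Keep any comparison of complications by completion optional, exploratory and labelled non-causal.

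The cost is small: item 1 uses existing output, item 2 is a short checklist, and items 3 to 5 are text. Completion may be self-reported and will probably be missing for patients already followed, and the objective becomes more modest. If completion cannot be recovered at all, items 1 and 4 still work alone.
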